HIV Risk Reduction Intervention for Transwomen with Intimate Partner Victimization:

Statistical Analysis Plan

Descriptive statistics will be used to characterize the study sample and compare baseline differences between intervention conditions. Fidelity to intervention protocols will be assessed using adherence and competence ratings on approximately 5% of all completed sessions, balanced across peer counselors and study. Feasibility will be quantified based on retention and attrition rates, which will be visualized in a CONSORT diagram.

To explore the preliminary efficacy of the intervention, mean values for key study outcomes (i.e., empowerment, IPV frequency, PTSD symptoms, depressive symptoms, and HIV vulnerability) will be plotted across study time points (baseline, post- intervention, 4-month, and 6-month follow-ups). We additionally will test for intervention effects using intent-to-treat models with all available data. Linear mixed models (LMMs) with maximum likelihood estimation will be used for continuous outcomes (e.g., empowerment, PTSD symptoms, and depressive symptoms). Count-based outcomes (e.g., past-2-month frequency of IPV, past-60-day number of HIV-vulnerable sex acts) will be dichotomized to indicate any vs. no occurrence (0 = none, 1 = any instance). These binary outcomes will be modeled using GLMMs with a binomial distribution and logit link function. All models will include fixed effects for condition, time, and condition \times time interactions. Any significant baseline demographic differences will be included as covariates in the final models. An unstructured covariance matrix will be used to account for within-participant correlations across time points.

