- Retention strategies: close communication and collaboration with CBOs that serve local TW and hiring an outreach specialist from within the local trans community.

Procedures

- Pilot STARS among TW ($n=5-8$) with elevated HIV risk and IPV.
- Elicit feedback via exit interviews (structured informant interview and evaluation surveys) to finalize STARS protocol and research procedures.
- Refine and finalize STARS manual, interventionist training protocol, and fidelity scales using participant feedback and acceptability and feasibility metrics.

Analysis

- Detailed notes of IDI exit interviews will be analyzed (consider recording) to review feedback and make final adjustments
- At the end of phase 2, compute descriptive data on all target outcomes in Table 1 and discuss how actual outcomes compare to target outcomes.
- Discrepancies will result in: 1) investigation of the reason for failure to meet this outcome, and 2) discussion among the research team.

[figure not shown]
Table 1. Target Outcomes	
Description (Assessment method)	Target
Feasibility and Acceptability— SAS, RT	
Acceptability (End of Intervention Survey; see C10.3)	Endorsing an average score of 3 or more (out of 5) for each rated intervention component)
Satisfaction (Client Satisfaction Questionnaire-8; see C10.3)	Average > 24 (or a mean score of 3 on each of the 8 items)
Intervention attendance	70% of all participants complete at the initial session and at least 2 of 3 booster sessions
Intervention Fidelity (see C8.4)	SAS and RT interventions achieve at least 80% adherence on a random subset of sessions
Safety	
Adverse events	No serious adverse events or injuries that are possibly, probably, or definitely related to study participation.
Feasibility and Acceptability—Research Procedures	
Recruitment rate	Average of 3-4 enrolled per month
STI testing procedures	80% of participants complete STI testing procedures at baseline and 70% at 6-month follow-up
Timeliness of assessments	80% of follow-up assessments occur within 3-weeks of due date
Completeness of self-report instruments and interviews	Self-report instruments have 80% of items completed and interviews 90% of items completed in 90% of cases
Retention rate	80% complete 3-mo and 70% complete 6-mo f/u assessments
Participant burden	Qualitative responses from exit interviews do not suggest undue burden of intervention or research procedures

Phase 3 (Years 1-4, October 2021 – July 2024)

General Overview

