- Pilot RCT phase: two-arm, randomized, controlled design with up to 50 TW.
- Participants will be followed for up to 6-months post enrollment with assessments taking place at T1: Baseline; T2: Post-intervention; T3: 4-months follow up; and T4: 6-months follow up.
- Refer to Figure 1 below for the study flow
- The control group will be given an attention and time-matched control condition focused on relaxation and stress reduction.
- Both the STARS intervention and the control protocol consist of two one-hour sessions held one week apart and two brief 20-30 minute booster sessions held two- and four-weeks after the 2nd hour long session.
- Both interventions are designed to be delivered by peer counselors. Requirements for peer counselors include identifying as trans women or trans feminine and having leadership roles in the trans community.

Figure 1. STARS - Phase 3: Randomized Controlled Trial (RCT) Study Flow Chart

Participants/eligibility

- Individuals will be eligible if they are:
 - (1) 18+ years old;
 - (2) Assigned male at birth but identify as female, transgender, or transfeminine;

- (3) Endorse at least one IPV incident during the previous 12 months based on the Conflict Tactic Scales-Revised (CTS-2; Straus, 2017) or the trans-specific IPV Scale (T-IPV Scale; Peitzmeier et al, in press);
- (4) Report at least one instance of condomless anal sex in the last 6-months.
- Individuals will be considered ineligible if they:
 - (1) Have been diagnosed with HIV or test positive for HIV.
- Individuals expressing interest in the research will undergo brief screening online or by telephone and then complete a more detailed in-person eligibility assessment prior to enrollment.
- All participants will provide informed consent prior to initiating the study protocol.

Recruitment

- All research activities will take place online via Zoom and/or in Providence, Rhode Island metropolitan area
- Multifaceted recruitment approach: online advertisements in social media for TW audiences, placing fliers in targeted venues, and conducting in-person outreach to agencies, clinics, bars and community events.
- Retention strategies: close communication and collaboration with CBOs that serve local TW and hiring an outreach specialist from within the local trans community.

Compensation

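### Continuous-outcome models use maximum likelihood with an unstructured four-visit covariance in at most 50 people and name no small-sample reference, so tests are mildly anti-conservative

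*SAP*

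**What the plan says.** The second paragraph of the SAP sets out the efficacy models.

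- Testing is planned alongside the plots of means: "We additionally will test for intervention effects using intent-to-treat models with all available data".
- Estimation: "Linear mixed models (LMMs) with maximum likelihood estimation will be used for continuous outcomes". The examples given are empowerment, PTSD symptoms and depressive symptoms.
- Mean structure: "All models will include fixed effects for condition, time, and condition"-by-time interactions.
- Covariance: "An unstructured covariance matrix will be used to account for within-participant correlations across time points". This sentence is not limited to the linear models.
- Outcomes reduced to any versus none: "These binary outcomes will be modeled using GLMMs with a binomial distribution and logit link function". No random effects are named.

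The protocol (section 4.2, Phase 3, General Overview) describes a "two-arm, randomized, controlled design with up to 50 TW", assessed at "T1: Baseline; T2: Post-intervention; T3: 4-months follow up; and T4: 6-months follow up". The retention target in Table 1 is "80% complete 3-mo and 70% complete 6-mo f/u assessments".

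Neither document gives an alpha, a choice between z, chi-square, t and F references, a degrees-of-freedom method, or REML.

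**The concern.** An unstructured matrix over four visits has 4 × 5 / 2 = 10 variance and covariance parameters, estimated here from at most 50 people. Two things then push p-values down. Maximum likelihood divides the residual sums of squares by N, ignoring the degrees of freedom spent on the means, so variances are understated. A chi-square or z reference also treats the estimated covariance as known. The SAP states the first and is silent on the second.

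The three continuous outcomes that the SAP names all go through this model. Empowerment may correspond to the protocol's primary outcome of IPV safety, though the SAP does not say so. Section 3 of the protocol presents the findings as groundwork for a larger trial, so the practical risk is that a chance difference looks somewhat more like support than it should.

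**Working it through.** The documents give no power or error-rate figure to reproduce.

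**Inputs.** From the documents: N = 50 at most, four visits, unstructured covariance, ML, 70% retention at 6 months. Assumed: two-sided 5%; time as a category, so the interaction has 3 df; no covariates; normal data. The 6-month contrast is the arm difference in change from baseline to 6 months.

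**Complete data (exact).** With a free mean for each arm and visit, the REML Wald statistic is Hotelling's T², and

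T² × (v − p + 1) / (p v) ~ F(p, v − p + 1), with v = N − 2 = 48.

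The ML Wald statistic is T² × N/(N − 2) = T² × 50/48 = 1.0417 T². The likelihood-ratio statistic is N ln(1 + T²/(N − 2)). These rates do not depend on the true correlations, the variances or the allocation ratio.

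For the interaction, p = 3 and T² × 46/144 ~ F(3,46):

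| Estimation and reference | Rejects when T² exceeds | Equivalent F(3,46) | Type I error |
|---|---|---|---|
| ML, chi-square (7.815) | 7.815/1.0417 = 7.502 | 2.397 | 8.0% |
| ML, F(3,48) (3 × 2.798 = 8.394) | 8.394/1.0417 = 8.058 | 2.574 | 6.5% |
| ML, likelihood-ratio (7.815) | 48 × (exp(7.815/50) − 1) = 8.120 | 2.594 | 6.4% |
| REML, chi-square | 7.815 | 2.496 | 7.2% |
| REML, F(3,48) | 8.394 | 2.681 | 5.8% |
| REML, Kenward-Roger (46 df) | exact test | exact test | 5.0% |

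For the 6-month contrast, p = 1 and T² ~ F(1,48). ML with z rejects at T² > 3.841/1.0417 = 3.688, giving 6.1%. ML with t on 48 df rejects at T² > 4.043/1.0417 = 3.881, giving 5.5%. The ML standard error is √(48/50) = 0.980 of its proper size, about 2% too small.

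**Share due to ML.** With chi-square, 8.03 − 7.15 = 0.88 points of a 3.0-point excess. With F(3,48), 6.54 − 5.78 = 0.76 points. The remainder comes from the reference.

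**Fewer participants.** Fifty is a ceiling. With 35 and complete data, the 3-df rates are 9.6% (ML, chi-square) and 7.3% (ML, F(3,33)); the 1-df z rate is 6.6%.

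**Dropout (simulated).** Null trials had 50 randomised, 25 per arm, and monotone dropout completely at random to 90%, 80% and 70% at the three follow-ups. The 90% is assumed, and the 80% target for 3 months was applied to the 4-month visit. Correlations were 0.5 (equal) or AR(1) 0.7 in one set, and 0.5 or 0.7 (equal) in a second. The Monte Carlo standard error was 0.2 to 0.5 points.

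| Test | First set | Second set |
|---|---|---|
| 3 df, ML chi-square | 9.2% to 9.9% | 9.4%, 9.6% |
| 3 df, ML F(3,48) | 7.9% to 8.3% | 7.8%, 7.9% |
| 3 df, REML Kenward-Roger | 5.1% to 5.5% | 5.3%, 5.3% |
| 6-month, ML z | 6.4% to 7.2% | 7.0%, 7.4% |
| 6-month, ML t(48) | not run | 6.2%, 6.7% |
| 6-month, REML Kenward-Roger | 4.9% to 5.3% | 5.0%, 5.5% |

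REML with chi-square, without a small-sample reference, still gave 8.2% to 8.3% for the 3-df test. The ML standard error of the 6-month contrast was about 5% too small.

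**Logit models.** With one 0/1 value per person per visit, the eight fixed effects already fit the eight arm-by-visit proportions. Suppose the unstructured matrix is read as four visit-level random effects. Fixing all four variances at 2, 4, 8 or 16 then moves the 6-month odds ratio from 0.55 to 0.49, 0.40 and 0.30, with a log-likelihood loss of at most 0.0002. Assumed inputs: event probability 50%, true variance 2, equal latent correlation 0.7. This is a likelihood calculation; no packaged routine was run. Residual-side or GEE, random-intercept, and intercept-plus-slope readings are estimable. A conditional odds ratio of 0.55 corresponds to a marginal 0.60 to 0.70, a difference of about 0.1 to 0.3 standard errors.

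**The case against.** The strongest reply is that most of the excess is not in the SAP's words. The plan states ML, which adds under 1 point; it does not state a chi-square reference, and many programs would supply t or F. A reader might infer that the false-positive rate is 8% to 10%. The documents do not support that as a general figure: with complete data at N = 50 it holds only for the low end, with a chi-square reference, the joint 3-df test and an alpha of 5%, none of which the SAP specifies. The higher values need dropout or fewer participants. This part of the reply stands. What remains is that ML exceeded 5% under every reference tried, so a favourable software default reduces the excess without removing it.

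Second, nothing is gated on a p-value. Section 3 of the protocol puts the interest in the pattern of results, the SAP presents the tests as exploring preliminary efficacy, and the Table 1 targets concern feasibility, acceptability and safety. This also stands and limits the weight of the point.

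Third, a reader might conclude that the binary-outcome models cannot be fitted. Only one of the four readings fails, and the estimable ones differ little. That is missing detail, not a demonstrated error.

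**Conclusion.** The point holds and is minor. At N = 50 with complete data, type I error is 6.4% to 8.0% for the 3-df test and 5.5% to 6.1% for the 6-month contrast. With dropout to 70% it is about 8% to 10% (F(3,48) to chi-square) and 6% to 7%. The direction is secure for every reference tried; the size depends on the reference that the SAP leaves open.

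The figures assume a nominal 5%, categorical time and no covariates; those with dropout also assume 1:1 allocation and dropout completely at random. If time were linear, coded 0, 1.5, 4 and 6 months, the 1-df ML z rate would be 7.3% with complete data and 8.5% to 9.0% with dropout. Kenward-Roger would give 5.4% and 5.6% to 5.9%, so it would be close to nominal but not exact.

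The documents do not support reading this as a threat to the trial's main aims. The consequence is a slightly over-optimistic efficacy signal. The logit-model question is a request for clarification only.

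**What to change.** Replace maximum likelihood in the SAP with REML and Kenward-Roger degrees of freedom for the continuous outcomes, and keep the unstructured matrix. Both parts are needed: REML with chi-square still gives 7.2% with complete data. State the nominal alpha, or say that p-values are descriptive.

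A simpler substitute covariance, such as heterogeneous AR(1), is not needed on this evidence. ML and REML converged in all 20,000 main simulated trials, that structure takes no account of the unequal visit spacing, and its error rate was not checked.

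Add one sentence on how the covariance statement applies to the logit models: name one estimable structure, and exclude four visit-level random effects.

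The cost is SAP wording and slightly wider intervals. For the 6-month contrast at N = 50 with complete data, the ratio to the ML z interval is (2.011/1.960) × √(50/48) = 1.026 × 1.021 = 1.047, or 4.7% wider. With dropout it is 7% to 8% wider; with linear time, 9% to 12%.

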- Participant reimbursement: Participants will have an opportunity to earn up to \$250 in total – they will receive \$50 for completing the T1: baseline assessment; \$50 for the T2: post-intervention assessment, \$25 for the exit interview; \$50 for the T3: 4-month follow up; \$50 for the T4: 6-month assessment; and a \$25 bonus if they complete all four assessments (T1-T4).
- Participants will be given the option to receive their compensation in the form of an Amazon gift card or on a VISA clincard.

Procedures

- Conduct a randomized pilot trial of STARS in 50 TW with elevated HIV risk and IPV to demonstrate the (a) feasibility, (b) acceptability, and (c) safety of the intervention.
- Examine preliminary evidence that relative to an attention and time matched control, STARS will result in improvements in our:
 - Primary outcomes;
 - Secondary outcomes; and
 - Mechanisms of change consistent with the theoretical foundations of the intervention, including greater perceived gender affirmation, and increases in empowerment and self-efficacy.
- Test, diagnose and (if positive) treat baseline STIs (and HIV) prior to initiating the STARS program. The research staff will work with participants to find gender-affirming health care clinics in their area that provide free or low-cost STI and HIV testing. Participants will be encouraged to

get tested for STIs as part of the research study; however, STI testing is not a requirement for participation.

- Complete a baseline behavioral and psychosocial baseline survey assessments administered via ACASI. Refer to the Phase 3 RCT Measures document for the complete list of standardized measures administered at baseline and at follow up.
- Upon completion of the baseline assessment, participants will be randomized to either the Intervention (STARS) condition or to a time-attention matched control (see details below).
 - **STARS Intervention** (*the final version of STARS was developed through an iterative process and refined/finalized by findings from Phases 1 and 2*)
 - Participants randomized to STARS will participate in a brief intervention immediately following the baseline (BL) assessment consisting of two one-hour sessions held one week apart and two brief 20-30 minute booster sessions held two- and four-weeks after the 2nd hour long session.
 - Participants will develop personalized risk reduction plan (RRP), which will include participants identifying “next steps” for reducing their HIV and IPV related risks.

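### For the any/none IPV and sex-act outcomes, the SAP models baseline as a free response in each arm and never conditions the arm effect on it; if the condition-by-time term is the test, this costs power

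*SAP*

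**What the plan says.** The SAP says "Count-based outcomes (e.g., past-2-month frequency of IPV, past-60-day number of HIV-vulnerable sex acts) will be dichotomized" and modelled with a binomial distribution and logit link. Every model has fixed effects for condition, time and condition by time, with an unstructured covariance across visits. Its only rule for adding covariates is "Any significant baseline demographic differences will be included as covariates in the final models". It names no primary time point and does not say which coefficient or contrast tests the intervention.

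Protocol section 4.2 (Phase 3) gives the visits as "T1: Baseline; T2: Post-intervention; T3: 4-months follow up; and T4: 6-months follow up", and the SAP lists the same four study time points. On the natural reading baseline is therefore a level of time and a response in the model. The protocol also says "Upon completion of the baseline assessment, participants will be randomized", so the baseline value is fixed before allocation.

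The design is "two-arm, randomized, controlled design with up to 50 TW". The retention target in Table 1 is "80% complete 3-mo and 70% complete 6-mo f/u assessments".

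**The concern.** Randomisation makes the two arms equal at baseline in expectation. A model that gives each arm its own baseline log-odds spends information estimating a difference known to be zero on average. The condition-by-time term at 6 months is the 6-month arm difference minus the baseline arm difference, so it carries the sampling error of both. Conditioning on baseline avoids this and also uses whatever baseline predicts about follow-up.

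IPV frequency is a protocol primary outcome, and these binary models are the only tests the SAP describes for count-based IPV and sex-act outcomes. With at most 50 women, a real effect is more likely to be missed, and the estimate carried into the later large trial is less precise than the same data allow. Leaving the contrast unnamed also lets the apparent strength of evidence depend on a choice made after the data are seen.

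**Working it through.** The documents state no power, alpha, event rate, correlation or effect size, so there is no figure to reproduce.

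**Inputs from the documents:** up to 50 women; 70% retained at 6 months, so 0.70 × 50 = 35; four visits.

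**Assumed:** 1:1 allocation (25 per arm at baseline, 17.5 at 6 months), two-sided 5% test, and all event rates, correlations and effects.

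**Step 1: why the change contrast is noisier (hand calculation).** The large-sample variance of one arm's log-odds is 1/(n·p·(1−p)). Assume 80% any at baseline in both arms, and 72% versus 35% at 6 months.

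- 6-month arm difference: ln(0.72/0.28) − ln(0.35/0.65) = 0.944 + 0.619 = 1.563.
- Its variance: 1/(17.5·0.72·0.28) + 1/(17.5·0.35·0.65) = 0.283 + 0.251 = 0.535 (unrounded sum).
- Variance of the baseline arm difference: 2/(25·0.8·0.2) = 0.500.
- Covariance of the two, for a correlation φ between the any/none indicators within a woman: φ·[1/(25·√(0.16·0.2016)) + 1/(25·√(0.16·0.2275))] = 0.432φ.
- Variance of the change contrast: 0.535 + 0.500 − 0.865φ.

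Power is Φ(1.563/SE − 1.96). The plain 6-month contrast gives 57%. The change contrast gives 34%, 39% and 47% at φ = 0, 0.2 and 0.4. It is noisier unless φ exceeds 0.500/0.865 = 0.58. For a smaller effect (70% versus 50%), the same formulas give 22% for the plain contrast and 13%, 15% and 18% for the change contrast.

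**Step 2: simulation of the models.** Counts over four visits were generated from gamma-Poisson models, 25 per arm, with retention falling to 70%, and analysed with random-intercept logit models. Sets A, B and C used 1,500, 500 and 400 runs per row, so simulation error is about 1, 2 and 2.5 points. Correlation is between baseline count and later any/none status. Entries are power in %; a dash means not run or not recorded.

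| Row | 6-month any, by arm | Corr. | Change contrast | Plain 6-month contrast, planned model | Common baseline | Follow-up with log(1 + baseline count) |
|---|---|---|---|---|---|---|
| A1 | 72 v 35 | 0.4 | 49 | – | 69 | 74 |
| A2 | 59 v 22 | 0.4 | 47 | – | 67 | 74 |
| A3 | 67 v 23 | 0.2 | 55 | – | 79 | 80 |
| B1 | 79 v 39 | 0.42 | 50 | 70 | – | 74 |
| B2 | 79 v 53 | – | 28 | – | – | 43 |
| B3 | – | 0.47 | 50 | 61 | – | 72 |
| B4 | – | 0.30 | 46 | 70 | – | 72 |
| C1 | 76 v 35 | 0.41 | 54 | 73 | 74 | 79 |
| C2 | 88 v 42 | 0.25 | 55 | 89 | 88 | 90 |
| C3 | 86 v 63 | 0.44 | 30 | 41 | 45 | 48 |
| C4 | 85 v 39 | 0.43 | 65 | 88 | 90 | 93 |

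- Last column minus change contrast: 15 (B2) to 35 (C2).
- Common baseline minus change contrast: 15 (C3) to 33 (C2). This step uses no count.
- Last column minus common baseline: 1 (A3) to 7 (A2). This is what the count adds.
- Last column minus plain contrast: 1 (C2) to 11 (B3).

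Under no effect, set A rejected in 6.1%, 6.1% and 6.4% of runs (change contrast, common baseline, baseline count). Set B rejected in 9% for both the change contrast and the baseline-count model. The gain is therefore not bought with extra false positives.

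**Step 3: smaller effects and a different count model.** Poisson-lognormal counts were used here. With a rate ratio of 0.5, 50 women and 30% missing at 6 months, the mixed model gave 10–13% for the change contrast and 11–16% for the plain contrast, a gap of 1 to 4 points. At a rate ratio of 0.35 it gave 19% and 32%. A simpler marginal analysis at 18 per arm and rate ratio 0.5 gave 7–11% for the change contrast and 18–20% with the baseline count. In those marginal runs, at 18 or 25 per arm, adding the count to the 6-month logit contrast moved power by −3 to +7 points.

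**The case against.** The strongest reply is that the planned model already contains the remedy. It yields the plain 6-month arm difference as well as the change contrast, and against the former the gain is mostly small. That is correct, and it is why the large figure is conditional on the interaction being the test. It does not remove the point, because the SAP leaves the choice open.

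Baseline is also not ignored. Its any/none value is in the model as the first response, linked to follow-up through the covariance matrix. That stands too: what is missing is conditioning on it.

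A reader might infer that reducing the baseline counts to any/none is what costs the power. Step 2 does not support this: the count adds 1 to 7 points there, and −3 to +7 in the marginal runs. Nor do the documents show that nearly all women are positive at baseline. Entry requires "Endorse at least one IPV incident during the previous 12 months", on the CTS-2 or the T-IPV Scale, whereas the outcome covers 2 months and the protocol assesses it with the CASr-SF and the T-IPV Scale. Item scoring is in a separate measures document.

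Finally, the simulations used a random intercept, not the SAP's unstructured covariance, and mostly large effects. The trial is a pilot to demonstrate feasibility, acceptability and safety, with efficacy explored for a pattern of results. These limits hold, and they reduce the weight of the point. But the SAP does say it will test for intervention effects, and the results are meant to prepare a larger trial.

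**Conclusion.** The point holds in a limited form. For the any/none IPV and HIV-vulnerable-sex-act outcomes, the tested effect is not named and is not conditioned on a baseline value that precedes randomisation. If the condition-by-time term at 6 months is the test, the loss is about 15 to 35 power points under large assumed effects, and it can shrink to a few points with small effects and about 35 completers. If the plain 6-month arm difference is the test, conditioning on baseline gains about 1 to 11 points. The main cause is the separate baseline log-odds per arm; the count contributes about 0 to 7 points. Every figure rests on assumed rates, correlations, effects, alpha and allocation.

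Two further readings should be set aside. The trial does not miss a stated power, because it states none. And the protocol's CR-HIV primary outcome is outside this point: it is binary by definition and built from partner status and PrEP use as well as condomless sex, so it is not a dichotomised count. Whether the follow-up outcome should be dichotomised at all is a separate question, not settled here.

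**What to change.** In the SAP, state that the tested effect for each binary outcome derived from a count is the condition effect at each follow-up visit, conditional on baseline. Specify one of two forms:

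1. Model T2 to T4 as the responses, with condition, visit and condition by visit, and include log(1 + the woman's own baseline count) as a pre-specified covariate whether or not the arms differ on it.
2. Keep T1 as a response but constrain the baseline mean to be common to both arms. This retains every randomised woman with a baseline assessment.

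Report the adjusted effect at each visit with its interval.

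The cost is a sentence or two in the SAP and no new data. The first form adds one parameter, and women with no follow-up visit leave the model. They carry almost no information on the contrast, but the SAP's commitment to intent-to-treat with all available data would need a matching remark. The second form avoids that and recovers most of the gain.
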